### Randomization

Randomization will be done for the allocation to one of the two different adjuvant combinations (arms A or B). The volunteers will be allocated to one of the two adjuvant arms per group at random using a Mersenne-Twister random number generator implemented in R through the command `sample()` and a pre-specified seed.

### Sample size

STOP-TRANS is an exploratory first-in-human study with the objective to identify large safety and tolerability signals. In addition, SMFAs are done to provide a first proof-of-concept. The study is largely descriptive and is intended to provide primarily safety data of 2 dose levels of R0.6C combined with 1 or 2 adjuvants given 4 times over 24 weeks. Comparative statistics will be performed but will have low power to detect anything other than very large differences between the groups. In total 32 participants will receive R0.6C. Based on a binomial distribution, this means that the probability to detect at least one clinically significant event (e.g. a serious adverse reaction) during vaccination with a power of 90% is 7%.

Furthermore, if we assume an effect size of 75% TRA at 14 days after the fourth R0.6C vaccination (I4+I4) compared to baseline (I1-I1), with the subject size of  $n=8$  per dose/adjuvant arm we will have an empirical power of >99% ( $\alpha=0.05$ ) to detect this, based on calculations and assumptions as described in the next paragraph.

### Estimation of empirical power for an analysis of transmission reducing activity under different assumptions

#### The simulation algorithm

1. We generate  $n_0$  subjects in the control (pre-treatment) group and  $n_1$  subjects in the treatment (post-treatment) group with a variable  $x_i$  to indicate whether the subject is in the control group ( $x_i = 0$ ) or in the treatment group ( $x_i = 1$ ).
2. We generate  $m$  mosquito dissections for each subject.
3. We simulate subject-specific random intercepts ( $z_i$ ) from a normal distribution with a mean of 0 and a specified standard deviation  $\sigma$ , i.e.  $Z \sim N(0, \sigma)$ .
4. Lastly we generate the oocyst counts ( $y_{ij}$ ) for each subject  $i$  and mosquito  $j$  using a negative binomial distribution such that  $Y \sim NB(\mu, \theta)$  where  $\theta$  is the anticipated dispersion parameter and  $\mu_{ij} = \exp(\beta_0 + \beta_1 x_{ij} + z_i)$  where  $\beta_0$  is the anticipated mean of the log oocyte counts in the control group and  $\beta_1$  is the anticipated regression coefficient used to estimate the TRA, such that

$$\beta_1 = \log\left(1 - \frac{TRA}{100}\right).$$

#### The model

To analyze the simulated data, we make the of the *mgcv* package in R. We run a Generalized Additive Mixed Model such that,

$$\log(y) = \beta_0 + \beta_1 x + z_i.$$

From each simulated dataset, we estimate the  $TRA = \left(1 - \exp\left(\hat{\beta}_1\right)\right) \times 100$  and  $p$  (the p-value) of the test for whether  $\beta_1$  is significantly different from 0. We then report the average  $TRA$  across simulations, which should be close to the anticipated value, and the empirical power which we define as the percentage of  $p$ 's less than 0.05.

#### Simulation results

We chose  $m = 20$  as the standard amount of mosquito dissections per subject. We used a previous study (NL69779.091.19) to extract anticipated values for the mean log oocyst count in the control group, the dispersion parameter  $\theta$  and the standard deviation of the random effects  $\sigma$ . i.e.  $\beta_0 = 3.7037$ ,  $\theta = 4.451$  and  $\sigma = 0.64$ . For the anticipated  $TRA$  (and thus anticipated  $\beta_1$ ) we used a range of assumed values, i.e.  $TRA = (25\%, 50\%, 75\%)$ . We also varied the number of people in the control

and treatment groups, i.e.  $n_0$  and  $n_1$ . The tables below show the empirical power under these scenarios.

TRA = 25%	<math>n_1</math>					
<math>n_0</math>	5	6	7	8	9	10
10	17.0	18.4	17.4	18.4	18.2	19.0
11	17.2	15.8	16.6	17.6	19.6	19.4
12	17.0	17.6	18.2	18.4	19.4	19.2
13	17.2	16.4	17.6	17.4	20.6	19.6
14	16.6	17.8	19.8	20.2	19.4	20.2
15	15.4	17.4	18.8	19.4	20.8	22.6
16	14.6	15.2	17.8	19.8	20.4	21.0
17	14.4	15.8	18.6	19.0	20.6	22.4
18	14.4	16.2	18.2	18.8	21.0	22.6
19	17.4	19.0	18.6	19.4	22.2	24.8
20	15.8	17.8	19.4	22.2	25.8	26.8

TRA = 50%	<math>n_1</math>					
<math>n_0</math>	5	6	7	8	9	10
10	52.0	57.0	60.4	63.8	64.4	67.0
11	54.2	58.8	62.4	63.8	65.2	69.6
12	55.0	59.4	62.8	65.4	69.2	70.6
13	54.6	58.2	63.6	67.0	69.4	71.8
14	58.4	62.4	64.8	68.2	70.4	73.0
15	55.6	59.2	65.0	66.6	70.4	74.0
16	55.2	60.4	64.0	68.0	71.6	75.8
17	54.6	60.6	66.8	69.8	75.8	78.2
18	54.2	61.6	67.8	72.2	75.6	78.4
19	59.6	66.8	71.0	76.8	78.8	81.6
20	61.8	68.2	72.8	78.6	80.6	82.8

TRA = 75%	<math>n_1</math>					
<math>n_0</math>	5	6	7	8	9	10
10	97.2	99.0	99.6	99.8	99.8	100.0
11	98.2	99.6	99.8	99.6	99.6	100.0
12	98.4	99.2	99.2	99.8	100.0	100.0
13	97.4	99.0	99.6	99.8	100.0	100.0
14	96.6	98.8	99.2	99.8	100.0	100.0
15	97.8	99.2	99.8	100.0	100.0	100.0
16	98.4	98.8	99.6	99.8	100.0	99.8
17	99.4	99.8	100.0	100.0	100.0	100.0
18	99.0	100.0	100.0	99.8	100.0	100.0
19	99.2	99.6	99.6	100.0	100.0	100.0
20	99.0	99.2	99.8	100.0	100.0	100.0

### Data capture and transfer

Designated trial staff will enter the data required by the protocol into the electronic CRF (eCRF) according to the Data Management Plan. An external monitor will review the data entered into the eCRFs by investigational staff for completeness and accuracy and will instruct the site personnel to make any required corrections or additions. After study close out by the monitor, the eCRF database will be locked by the PI of the study. Data can be exported from the database in Microsoft Excel files for further use in statistical analysis.

### Statistical interim analyses and stopping guidance

There are no pre-defined criteria for study termination in this clinical trial based on SMFA or other biological results. Safety and reactogenicity data will be evaluated by a safety monitoring committee (SMC) after the first R0.6C administration in each group before proceeding to the next group. A summary report of adverse events (AEs) will be provided to the SMC after all groups have completed follow-up (I4+84). The study may be placed on safety hold at any time for the following reasons:

- On advice of the safety monitor;
- On advice of the Principal/Clinical investigators;
- On advice of the SMC;
- On advice of the CCMO;
- If holding rules are met (see below).

If the following holding rules are met, administration of R0.6C will be held for all remaining administrations in that dosage group and subsequent groups:

- One or more participants experience a serious adverse event (SAE) that is determined to be at least possibly related to the administration of R0.6C
- Two or more subjects experience a grade 3 adverse event (local, clinical systemic or laboratory systemic) possibly, probably or definitely related to R0.6C administration and persisting at grade 3 for >72 hours

If considered necessary by the investigators or SMC, remaining administrations in lower dosage groups may also be put on hold.

### Statistical Software

- Safety data analysis will be performed in IBM SPSS (latest version available), or R. To ensure reproducibility an R script or SPSS syntax file will be created.
- SMFA data analysis will be performed using an online data analysis tool developed to estimate transmission reduction in transmission trials with reduction in oocyst density as an endpoint (Add ref: Ramjith, [name] et al. *Frontiers in immunology*, accepted for publication) [https://bousema-lab.shinyapps.io/transmission\\_sample\\_size](https://bousema-lab.shinyapps.io/transmission_sample_size).
- R0.6C antibody kinetics will be analyzed using standard non-compartmental methods using the Phoenix WinNonlin software package.
- If significant transmission reducing activity is measured in the SMFA, the relationship between serum antibody quantities and transmission reducing activity in SMFA will be assessed using standard compartmental pharmacokinetic models and empirical and mechanistic pharmacokinetic-pharmacodynamic models using the non-linear mixed effects modelling software package NONMEM 7.4, using Piraña 2.9 as an interface and R for data processing.

## Statistical Principles

### Confidence intervals and P values

Two-sided p values less than 0.05 will be considered statistically significant. Adjustments for multiple comparisons will be implemented where appropriate.

Where applicable, normally distributed continuous outcomes will be presented as mean with 95% CI or standard deviations. Continuous outcomes that are not normally distributed will be transformed using a suitable transformation before reporting 95% CIs or will be presented with median and interquartile ranges. For discrete (or count) data we will find interquartile ranges. Binary data will be presented as counts and proportions.

### Adherence and protocol deviations

The SAP will be followed even if data are missing. For the safety analysis, data from all subjects who received at least one dose of R0.6C in the study will be included. Subjects who miss an appointment date will not be removed from the study. Rather, their appointment and laboratory values will be recorded by appropriate missing value notation in the clinical database. Non-analyzable data will be documented in the deviations. A best-worst case sensitivity analysis may be performed.

## Study Outcome Measures

### Outcome Definitions

(Protocol section 8.1).

Primary safety Endpoints:

- 1) The number of serious adverse events and solicited and unsolicited grade 3 adverse events possibly, probably or definitely related to the vaccine in the period from first R0.6C administration up to 84 days after the last immunization.

Primary efficacy endpoints:

- 2) The functional transmission reducing activity in the standard membrane feeding assay of volunteer sera collected two weeks after the fourth R0.6C immunization (I4+14), compared to baseline (I1-1) within each of the four dose-adjuvant groups.

Secondary safety endpoints:

- 3) The number of solicited and unsolicited grade 1 and 2 adverse events possibly, probably or definitely related to the vaccine in the period from first R0.6C administration up to 84 days after the last immunization.

Secondary efficacy endpoints:

- 4) The TRA at other timepoints (I1+14, I2+14, I3+14, I3+111 [I4-1], and I4+84) compared to baseline (I1-1) in each of the four dose-adjuvant groups.
- 5) The anti-6C antibody quantity in volunteer sera collected two weeks after fourth R0.6C immunization (I4+14) and at other time points (I1+14, I2+14, I3+14, I3+111 [I4-1], and I4+84)

compared to baseline (I1-1) in each of the four dose-adjuvant combinations, as determined by ELISA.

#### Exploratory Endpoints:

- 6) The functional TBA in the SMFA of volunteer sera collected at different time points compared to baseline (I1-1) in each of the four dose-adjuvant combinations.
- 7) The anti-6C antibody decay rate following R0.6C immunization for each of the four dose-adjuvant combinations.
- 8) The anti R0.6C and anti-R0 antibody quantity in volunteer sera collected at different time points in each of the four dose-adjuvant combinations.
- 9) The cellular immune responses in volunteers samples collected at different time points in each of the four dose-adjuvant combinations.
- 10) The difference in TRA between the two dose groups (30 or 100 $\mu$ g R0.6C) and/or between adjuvant groups (alhydrogel and alhydrogel+Matrix-M).
- 11) The difference in peak anti-6C antibody quantity between the two dose groups (30 or 100 $\mu$ g R0.6C) and/or between adjuvant groups (alhydrogel and alhydrogel+Matrix-M).

## Analysis Methods

### Trial population

For the safety analysis, data from all subjects who received at least one dose of R0.6C and for whom safety data are available will be included.

### Recruitment

- Recruitment data will be summarized in a flow diagram.

### Screening data

- Screening data will be summarized for each study group. Eligibility criteria are specified in protocol section 5.2 and section 5.3.

### Withdrawal and follow-up

- Procedures for withdrawal of individual subjects are described in protocol section 8.4. Should reasons for withdrawal be known, these will be described, including the timing of withdrawal.

### Baseline patient characteristics

- Demographic data will be summarized by descriptive statistics per dose/adjuvant group and will include the total number of observations (n), plus the mean, standard deviation (SD) and range for normally distributed continuous variables and number and percentages for dichotomous variables. This data will be tabulated.

- Where applicable, continuous outcomes that are not normally distributed will be transformed using a suitable transformation before reporting means and SDs. Where a suitable transformation cannot be found, the mean and SDs will be substituted with the median and interquartile ranges. For discrete (or count) data we will report the medians and interquartile ranges. Binary data will be presented as counts and proportions or percentages.

## Analyses in relation to endpoints

### Safety outcome analyses

- For each solicited (local or general) adverse event type, possibly, probably or definitely related to the R0.6C vaccinations, the number and proportion of subjects experiencing that AE within the protocol-defined timeframe will be tabulated by severity grade for each dose/adjuvant group and for the entire study population. This will also be tabulated for subjects experiencing any solicited local, any solicited general and any solicited AE (see example table below). Where applicable, we will compare these proportions between groups. Relatedness (possibly, probably or definitely) and duration of solicited AEs to R0.6C vaccinations may also be presented. (Endpoints 1 and 3).
- For each unsolicited adverse event type (categorized by ICD-10) that is possibly, probably or definitely related to the R0.6C vaccinations, the number of adverse events per dose group and overall study population will be described categorized by severity grade. Translation from ICD-10 coding to MedDRA terms may be performed where necessary. (Endpoints 1 and 3).
- The proportion of individuals with grade 1, 2 and 3 adverse events may be compared between groups.
- The total number of grade 1, 2 and 3 adverse events as count data may be compared between groups.
- Individual serious adverse events (SAEs) will be summarized, including relatedness to R0.6C vaccinations (Endpoint 1).
- Withdrawals due to AEs/SAEs will be summarized per group.

Table 1 - Descriptive statistics for subjects experiencing solicited AEs

		30µg R0.6C/AI OH		30µg R0.6C/AI OH + Matrix-M		100µg R0.6C/AI OH		100µg R0.6C/AI OH + Matrix-M		All	
		#Subjects	%	#Subjects	%	#Subjects	%	#Subjects	%	#Subjects	%
Local AE1	Grade 1										
	Grade 2										
	Grade 3										
	Any grade										
Local AE2	Grade 1										
	Grade 2										

	...										
	....										
Any local AE*	Grade 1										
	Grade 2										
	Grade 3										
	Any grade										
Systemic AE1	Grade 1										
	Grade 2										
	...										
Any systemic AE*	Grade 1										
	Grade 2										
	...										
Any AE*	Grade 1										
	Grade 2										
	...										

\* List (only) highest grade AE per subject

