10. STATISTICAL ANALYSIS

All data will be collected and verified prior to analysis. All data will be analysed in accordance with the Statistical Analysis Plan. Final analyses of all data will occur after study completion and final verification of data according to GCP. All data analyses will be conducted using IBM SPSS, R, SAS or Graphpad using the latest version available. Detailed statistical procedures, listings, table shells, and figures will be provided in a SAP prior to analysis. The SAP will be finalized before study close-out and database lock. The following key statistical components will be considered and a detailed description will be documented in the SAP:

- Primary and secondary endpoints and how they will be measured
- Statistical methods and tests that will be used to analyze the endpoints
- Strategy that will be used if the statistical test assumptions are not satisfied
- Indication of whether the comparisons will be using one-tailed or two-tailed *t*-test (with justification of the choice) and the level of significance to be used
- Identification of whether any adjustments to the significance level or the overall P-value will be made to account for any planned or unplanned subgroup analyses or multiple testing
- Specification of potential adjusted analyses and a statement with which covariates or factors will be included
- Planned exploratory analyses and justification of their importance
- Any subgroup effects with biological justification and support from within and outside the study

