10.1 Primary study parameter(s)

The number of subjects enrolled, completed, or withdrawn will be summarized. Reasons for withdrawal, when known, will be provided. Demographic data will be summarized by descriptive statistics and will include total number of observations (n), mean, standard deviation (SD) and range for continuous variables, and number and percentages for dichotomous variables. The primary safety, and reactogenicity outcomes will include all subjects who meet the eligibility criteria, received the study product R0.6C, and for whom safety data are available.

Safety endpoints

For the safety analysis, data from all subjects who received at least one dose of R0.6C and for whom safety data are available will be included. All analyses will be descriptive. Data will be presented by dose, overall/dose and overall/subject. Results will be summarized by study group. The percentage of subjects with at least one local AE (solicited or unsolicited), with at least one general AE (solicited or unsolicited) and with any AE during the solicited follow-up period will be tabulated with exact 95% CI (two-sided). No multiplicity adjustment will be implemented in analysis. The same calculations will be performed for AEs rated as grade 3.

The percentage of subjects reporting each individual solicited local and general AE during the solicited follow-up period will be tabulated with exact 95% CI. The same tabulation will be performed for grade 3 AEs and for AEs with relationship to R0.6C administration. The reports of unsolicited AEs will be reviewed by a physician and will be categorized by ICD-10. The percentage of subjects with at least one report of unsolicited AE and reported up to 28 days after R0.6C administration will be tabulated with exact 95% CI. The same tabulation will be performed for grade 3 unsolicited AEs and for unsolicited AEs with a relationship to R0.6C administration. SAEs will be described in detail. Withdrawals due to AEs/SAEs will also be summarized. Vital signs which are outside of the normal range and clinically significant will also be listed in tables. The frequency of signs and symptoms will be compared between groups with the chi-square test or fishers exact test. Serious adverse events (SAEs) occurring at any point during the trial will be summarized and relatedness to vaccine will be assessed.

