Any clinically important deviations in routine laboratory test results and/or vital signs as determined by the investigator will be listed. Isolated laboratory abnormalities will be reported as AEs if they are considered clinically relevant by the investigator. Vital signs which are considered clinically relevant by the investigator will be summarized. All adverse events will be listed by participant and will include details of onset time, duration, severity and relationship to the study product.

Efficacy endpoints

SMFA will be performed to determine TRA of R0.6C. Differences will be assessed by comparing mean values between time points using either a two-tailed student's t-test or a non-parametric equivalent. Paired tests will be used if pre-intervention values are compared with post-intervention values. For discrete variables (e.g. the number of positive assays), the chi-squared test or Fisher's exact test will be used (two-tailed).

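### The SAP commits only to summaries of vaccine-related AEs, without intervals, where the protocol also promises all-causality subject percentages with exact 95% CIs

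*SAP*

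**What the plan says.** Protocol 10.1 sets out the safety tables. Subjects with any local AE, any general AE and "with any AE during the solicited follow-up period will be tabulated with exact 95% CI (two-sided". For individual symptoms, "The percentage of subjects reporting each individual solicited local and general AE during the solicited follow-up period will be tabulated with exact 95% CI". Neither carries a causality condition. Related events come as an addition: "The same tabulation will be performed for grade 3 AEs and for AEs with relationship to R0.6C administration". For unsolicited events, "The percentage of subjects with at least one report of unsolicited AE and reported up to 28 days after R0.6C administration will be tabulated", again with exact 95% CIs and again followed by a separate table of related events. The same section promises a listing: "All adverse events will be listed by participant and will include details of onset time, duration, severity and relationship to the study product".

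The SAP, under Safety outcome analyses, begins its solicited bullet with "For each solicited (local or general) adverse event type, possibly, probably or definitely related to the R0.6C vaccinations" and then asks for the number and proportion of subjects by severity grade. Its unsolicited bullet covers each event type "that is possibly, probably or definitely related to the R0.6C vaccinations, the number of adverse events per dose group and overall study population". Both bullets are tagged to endpoints 1 and 3. The shell of SAP Table 1 has columns for number of subjects and percentage only. The SAP's general rule, under Confidence intervals and P values, is that binary data are shown as counts and proportions.

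On which document directs the analysis, Protocol section 10 says: "All data will be analysed in accordance with the Statistical Analysis Plan".

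**The concern.** The trial is open-label (Protocol 8.2) and has no placebo group (Protocol 4). Causality is decided by investigators who know the dose and adjuvant (Protocol 9.2.3). The boundary that decides entry to the SAP's tables is a fine one. Under Protocol 9.2.3 an event is *Possible* even when another cause is more likely, and *Unlikely* even when a link cannot be excluded. Several solicited general symptoms, such as headache, fatigue and myalgia (Protocol 9.2.2), are non-specific, so alternative explanations are easy to find.

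All-causality tables let a reader see how much of the result depends on that judgement. If only the SAP is programmed, those tables are not produced for non-serious events. The proportions that remain come from groups of eight with no statement of their precision.

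**Working it through.** **Side-by-side comparison of the two texts**

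| Item | Protocol 10.1 | SAP, Safety outcome analyses |
|---|---|---|
| Solicited AEs: causality | All, with related AEs as a further table | Related only |
| Solicited AEs: interval | Exact 95% CI | None stated |
| Unsolicited AEs: causality | All, with related AEs as a further table | Related only |
| Unsolicited AEs: unit | Percentage of subjects | Number of events |
| Unsolicited AEs: window | Up to 28 days after administration | None stated in the bullet |
| Unsolicited AEs: interval | Exact 95% CI | None stated |
| Grouping | By study group | Solicited: dose/adjuvant group. Unsolicited: dose group |

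The SAP does have two bullets on grade 1 to 3 AEs without a causality filter, but both are optional comparisons between groups.

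**The SAP's own safety figure**

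The SAP's Sample size section pairs 90% with 7% for 32 participants. Read as the true event rate at which at least one event is seen with 90% probability:
- 1 − (1 − 0.07)^32 = 0.902.
- Inverse: 1 − 0.10^(1/32) = 6.94%, which rounds to 7%.

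The figure reproduces, although the sentence swaps the roles of probability and power. It describes all 32 subjects together. For one group of 8 the same formula gives 1 − 0.10^(1/8) = 25.0%.

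**What the omitted intervals would show**

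Inputs: n = 8 per group (Protocol 5.4) and n = 32 overall. The event counts x are illustrative and do not come from the documents. Exact (Clopper-Pearson) limits are:
- lower = the 2.5% quantile of Beta(x, n − x + 1), or 0 if x = 0;
- upper = the 97.5% quantile of Beta(x + 1, n − x). For x = 0 this is 1 − 0.025^(1/n).

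| Count | Percentage | Exact 95% CI |
|---|---|---|
| 0/8 | 0% | 0 to 36.9% |
| 1/8 | 12.5% | 0.3 to 52.7% |
| 2/8 | 25.0% | 3.2 to 65.1% |
| 0/32 | 0% | 0 to 10.9% |
| 1/32 | 3.1% | 0.1 to 16.2% |

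Moving one subject's only event from *Possible* to *Unlikely* changes that group's cell in the related-only table from 1/8 to 0/8, a shift of 12.5 percentage points. In an all-causality table the cell would not move.

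**The case against.** There are five serious counter-arguments.

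*Unrelated events are not hidden.* A reader might infer that an event judged *Unlikely* would appear nowhere. The documents do not support that. Protocol 10.1 lists every AE by participant with its relationship to the product. The SAP summarises all SAEs and all withdrawals due to AEs or SAEs, and analyses laboratory abnormalities by participant. Protocol 9.5.3 gives the Safety Monitoring Committee AE summaries that are not limited to related events. This stands, and it narrows the loss to aggregate tables of non-serious AEs.

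*The endpoints themselves are defined by relatedness.* A reader might blame the SAP for making the primary safety result depend on unblinded causality calls. That dependence comes from the endpoint definitions in Protocol 8.1, and the SAP's filtered bullets implement them faithfully. All-causality tables would add a check without removing the dependence.

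*The SAP calls itself a supplement* (SAP, Purpose). Nothing in it expressly cancels the protocol's tables, so a reader should not infer a deliberate repeal. But Protocol section 10 directs analysis to the SAP, and the SAP's safety section neither repeats nor cites those tables. An analyst working from the SAP would not produce them.

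*Anyone can compute an exact interval from a count and a denominator.* This is true of the solicited table. It is not true of unsolicited AEs, because a number of events does not show how many subjects had one. The width of the intervals is a property of n = 8 and is not caused by the SAP. The SAP is also open about being descriptive and low-powered.

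*The dose-group wording may be loose drafting.* The neighbouring bullet and Table 1 use the four dose/adjuvant groups. Pooling the two adjuvants is therefore a possible reading and not a stated plan.

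**Conclusion.** The point holds as a specific departure of the SAP from the protocol. The SAP's committed solicited and unsolicited AE summaries are restricted to related events, its unsolicited output is a count of events where the protocol promises a percentage of subjects, and the exact 95% CIs are absent. What is lost is the group-level, all-causality incidence of non-serious AEs with intervals. Raw visibility of the events is not lost, and the handling of endpoints 1 and 3 is not wrong.

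The practical size follows from groups of eight: a zero count is compatible with a true rate of up to 36.9%, and one changed causality call moves a related-only cell by 12.5 points. This assumes that the analysis is programmed from the SAP as written and that all eight subjects in a group contribute safety data. How often causality calls will fall near the boundary is unknown. The matter should be put right in the SAP, but it does not threaten the trial's conduct or its primary definitions.

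**What to change.** In the SAP's Safety outcome analyses:
- Add tables regardless of causality, by the four dose/adjuvant groups, giving percentage of subjects with exact 95% CIs: any local, any general and any AE and each solicited AE in the solicited period, and unsolicited AEs up to 28 days after administration.
- Keep the related-only tables as a second set, labelled as serving endpoints 1 and 3.
- In the unsolicited bullet, replace the dose-group wording with dose/adjuvant group.
- Bring Table 1 into line with the text. Its title carries no causality filter although the bullet above it does, and its shell needs interval columns.

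If the narrower output is intended, the SAP should say so and justify the departure from Protocol 10.1.

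The cost is some programming and a few more table columns. The protocol already records all AEs with intensity and relationship, so no trial procedure changes.
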